3.1.5 Long Term Extension

The long term extension (LTE) period is optional and will include eligible subjects who have completed Day 85 (12-weeks of treatment) and who have consented to participate. Eligible subjects [platelet count $\geq 35,000/\text{mm}^3$ with at least a doubling of platelets from short-term baseline, or patients approved by the Study Director on a case by case basis who are close to a two-fold increase from short term baseline and/or have 30,000-35,000 $/\text{mm}^3$ platelets and absence of bleeding and any significant AEs as assessed on D71 or if more recent platelet count is available, based on the most recent platelet count or on the average of the two consecutive most recent platelet counts, whichever is higher], will receive a 1500 mg dose every other week for 24 weeks. Subjects who complete 24 weeks LTE will receive a taper regimen consisting of 1500mg dose on Day 190 and a final dose on Day 218 before entering the 24 week follow-up period (no treatment).

A separate informed consent must be signed by the patients to enter the LTE period.

3.2 Post Study Access to Therapy

At the end of the 12 week treatment study period, all eligible subjects in Cohort 3 and 4 will have the option to continue into the LTE period. The investigator should ensure that the subject receives appropriate standard of care to treat the condition under study.

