1.5.5 Other

Risks from the PK, PD, and clinical safety phlebotomy procedures are standard and include discomfort at the injection site, bleeding, bruising, and rarely blood clot formation, infection, and fainting. Furthermore, rescue medications are permitted in the study for severe bleeding or wet purpura or if the investigator thinks the patients is at immediate risk. These medications are to be given with the intended purpose of raising platelet counts.

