Early Decision Rule:

If there is not AE of interest observed, the early decision rule is the same the minimum requirements.

If there is one AE of interest observed, the early decision rule is shown below in Table 3.1.4-1, where W represent wait, i.e., not enough evidence to enable dose panel escalation, and E represents escalate.

If there are least two subjects with AE of interest, stopping rule is triggered, and subject cannot be treated at the next higher cohort.

Table 3.1.4-1: Decision Rule for Early Panel Escalation When There Is One Subject with AE of Interest (k=1)

Titration-Dose Evaluable Subjects (nH) ^a	Start-Dose Evaluable Subjects (nL) ^b								
	1	2	3	4	5	6	7	8	9
0	W ^c	W	W	W	W	W	W	W	E ^d
1	W	W	W	W	W	W	E	E	
2	W	W	W	W	W	E	E		
3	W	W	W	W	E	E			
4	W	W	W	E	E				
5	W	W	E	E					
6	W	E	E						
7	E	E							
8	E								

^a the number of subjects who are titrated and complete the evaluation period (2 weeks) starting from the titration’s first dose.

^b the number of subjects who develop AE of interest or complete the evaluation period (2 weeks) from the first dose but could not be classified into the “Titration-Dose Evaluable Subjects” group.

^c W: Wait

^d E: Escalate

Physical examinations, vital sign measurements, 12-lead electrocardiograms (ECG), and clinical laboratory evaluations will be performed at selected times throughout the dosing interval. Subjects will be closely monitored for adverse events throughout the study. Blood samples will be collected for up to 336 hours after study drug administration for pharmacokinetic (PK)

analysis. Approximately 910 mL of blood will be drawn from each subject during the short-term period (~162 days including Screening and follow up period). Less than 500mL of blood will be drawn during the LTE period.

The approximate duration of the short-term period is 23 weeks (approximately 162 Days). This includes a 21 day screening period, a 12 week treatment period and a 2 month follow up period. An extended screening period (up to 42 days) is possible but only with the approval of the Study Director, and all other eligibility rules and screening rules must still be met. If subject is eligible and opts to continue into LTE, the 2 month follow-up period will not be performed after the short-term period is completed and the subject will enter the LTE directly. If the subject opts not to enter the LTE, then a 2 month follow-up visit will be completed.

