3.6 Post Study Drug Follow up

In this study, increase in platelet count is a key endpoint of the study. Post treatment study follow-up is of critical importance and is essential to preserving subject safety and the integrity of the study. Subjects who discontinue study treatment must continue to be followed for collection of outcome and/or survival follow-up data as required and in line with Section 5 until death or the conclusion of the study.

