3.6.1 Withdrawal of Consent

Subjects who request to discontinue study drug will remain in the study and must continue to be followed for protocol specified follow-up procedures. The only exception to this is when a subject specifically withdraws consent for any further contact with him/her or persons previously authorized by subject to provide this information. Subjects should notify the investigator of the decision to withdraw consent from future follow-up **in writing**, whenever possible. The withdrawal of consent should be explained in detail in the medical records by the investigator, as to whether the withdrawal is from further treatment with study drug only or also from study procedures and/or post treatment study follow-up, and entered on the appropriate CRF page. In the event that vital status (whether the subject is alive or dead) is being measured, publicly available information should be used to determine vital status only as appropriately directed in accordance with local law.

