5.4.2 Secondary Efficacy Assessments

- Proportion of subjects achieving platelet count $\geq 50,000/\text{mm}^3$ with an increase of at least $20,000/\text{mm}^3$ from Short Term Day 1 and absence of bleeding
- Percent of visits with platelet count above $30,000/\text{mm}^3$ ($50,000/\text{mm}^3$ or $100,000/\text{mm}^3$). If subject entered study with baseline between $30,000\text{-}35,000/\text{mm}^3$ at Short Term Day 1,

determine percent of visits with platelet count above subject's Short Term Day 1 platelet count.

- Mean platelet count at each visit
- Mean change from baseline in platelet counts at each visit
- Mean fold change from baseline in platelet counts at each visit
- Time to response: time from starting treatment to achievement of CR or R.
- No response (NR): platelet count $< 30,000/\text{mm}^3$ or less than 2-fold increase of baseline platelet count or bleeding.
- Percentage of participants experiencing any bleeding episode and the total number of bleeding events.
- Subject's Bleeding Score (measured by the ITP-BAT Bleeding Assessment Test)
- Corticosteroid-dependence - the need for ongoing or repeated doses administration of corticosteroids for at least 2 months to maintain a platelet count at or above $30,000/\text{mm}^3$ and/or to avoid bleeding.
- The duration of response is measured from the achievement of a first measured CR or R until the loss of CR or R.
- Ability to maintain Response or Complete Response after stopping treatment.

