7.5.1 Derivation of Efficacy Endpoints

Primary efficacy criteria and response category:

- Response (R) - platelet count $\geq 30,000/\text{mm}^3$ and at least 2-fold increase from the baseline count and absence of bleeding.
- Complete Response (CR) - platelet count $\geq 100,000/\text{mm}^3$ and absence of bleeding.
- No Response (NR) - platelet count $< 30,000/\text{mm}^3$ or less than 2-fold increase of baseline platelet count or bleeding.
- Not Assessable (NA) - platelet count is missing or is excluded due to rescue medication.

Subject's best response is decided in the order of CR, R, NR, and NA.

Secondary efficacy criteria and response category:

- Clinically Significant Response - platelet count $\geq 50,000/\text{mm}^3$ with an increase of at least $20,000/\text{mm}^3$ from baseline and absence of bleeding.
- No Clinically Significant Response - platelet count $< 50,000/\text{mm}^3$, or increase of $\leq 20,000/\text{mm}^3$ from baseline, or bleeding.
- Not Assessable (NA) - platelet count is missing or is excluded due to rescue medication.

Absence of bleeding:

Absence of bleeding is defined as SMOG scores being zero for all the three major domains (Skin, visible mucosae, and organs) with ITP-BAT on the same day when platelet count is assessed.

Platelet data exclusion and rescue medication flag:

Platelet counts collected within 4 weeks after any rescue medication, though still shown in listing of figures of raw data, will be excluded from summarizing platelet and deriving subject response. To facilitate the exclusion, rescue medication flag may be derived and included in some analysis datasets and listings if at least one subject takes rescue medication after the first dosing during the trial. Rescue medication flag is set to Y (Yes) within 4 weeks after the day any rescue medication is administered, i.e., between rescue medication day and rescue medication day + 27, inclusively. It will be set to N (No) when otherwise.

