7.5.4 Response with primary efficacy criteria

The best response status over the entire study will be reported for all treated subjects with platelet at baseline, administered dose on day 1, and administered dose on day 57. For responders, treatment group, dose escalation status (Y/N), time to respond, time to peak response, and duration of response will be provided in a listing.

Response rates and number of subjects having dose escalated will be provided for each treatment group and all.

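### SAP response is scored over the whole study and excludes only counts within 28 days of rescue medication, so platelet rises from other ITP treatment can be credited to BMS-986004

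*Protocol*

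**What the plan says.** **Response window.** SAP 7.5.4 states: "The best response status over the entire study will be reported for all treated subjects". SAP 7.5.5 likewise gives response under the secondary criteria for the whole study. Neither stops at the last dose. Protocol 8.4.2 instead reports response rate by panel and treatment phase, naming the response and remission phases. Protocol 3.1 makes follow-up a separate third phase.

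**Counts off drug.** Protocol 3.6 states: "Subjects who discontinue study treatment must continue to be followed for collection of outcome and/or survival follow-up data as required". Protocol 3.6.1 adds: "Subjects who request to discontinue study drug will remain in the study and must continue to be followed for protocol specified follow-up procedures". For subjects who finish treatment, Protocol 3.1.4 states: "If the subject opts not to enter the LTE, then a 2 month follow-up visit will be completed". Protocol Table 5.1-2 schedules laboratory tests, with platelet count as an efficacy parameter, at Days 99, 113, 127 and 141.

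**Exclusion for other treatment.** SAP 7.5.1 removes one set of counts from the platelet summaries and from response: "Platelet counts collected within 4 weeks after any rescue medication". The flag runs from the rescue day to that day plus 27. The visible protocol describes rescue in Section 1.5.5: "rescue medications are permitted in the study for severe bleeding or wet purpura", or when the investigator sees immediate risk. The stopping rule in Protocol 3.1.3 is wider. It sets aside platelet rises due to rescue or to concomitant therapy.

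**Off-drug efficacy.** Protocol 5.4.2 lists "Ability to maintain Response or Complete Response after stopping treatment" and measures duration of response until R or CR is lost.

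**Other care.** Protocol 3.2, headed Post Study Access to Therapy, says: "The investigator should ensure that the subject receives appropriate standard of care to treat the condition under study". It gives no timing for that care.

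**The concern.** The study is open-label and has no control arm, so nothing separates a platelet rise caused by BMS-986004 from one caused by another ITP treatment except the rule on which counts are used. That rule names rescue medication alone. Best response is ranked CR, R, NR, NA, so one qualifying count at any visit is enough.

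The response rate is the protocol's secondary efficacy endpoint, and dose response is a secondary objective. SAP 6.2 groups results by starting dose. Under the protocol's assumed rates the lowest-dose cohort has the most non-responders, and the long-term extension is open only to cohorts 3 and 4. Subjects in cohorts 1 and 2 who finish treatment therefore all go to off-drug follow-up. Misattributed responses would tend to fall there, raising the low-dose rates and flattening the dose response. Time to peak, percent of visits above a threshold, duration and off-drug maintenance draw on the same counts.

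**Working it through.** **1. The plan's own figure.** Protocol 8.1 gives a 90% interval of (0.15, 0.70) for 4 responders of 10. The exact (Clopper-Pearson) limits are the 5% quantile of Beta(4, 7) and the 95% quantile of Beta(5, 6), which are 0.150 and 0.697. The stated interval is reproduced.

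**2. Effect of one misattributed responder.** With 10 subjects, 1/10 = 10 points. The exact 90% intervals are:
- 4/10: (0.15, 0.70)
- 5/10: (0.22, 0.78)
- 6/10: (0.30, 0.85)

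**3. Share of scheduled counts that are off drug.** From Table 5.1-2, post-baseline platelet days through Day 85 are 2, 4, 8, 15, 29, 43, 50, 57, 71, 72, 75, 78 and 85, which is 13. Follow-up adds 4. So 4/17 = 24% of scheduled days follow the last dose and can set whole-study response. SAP 2.1 describes a 4-week follow-up where the protocol has 8 weeks. On the SAP's length only Days 99 and 113 remain, giving 2/15 = 13%. Off-drug counts enter either way.

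**4. When the rescue flag lapses.** The flag ends on the rescue day + 27.
- Rescue on Day 85: flagged to Day 112. Days 85 and 99 are removed; Days 113, 127 and 141 count again.
- Rescue on Day 99: flagged to Day 126. Days 99 and 113 are removed; Days 127 and 141 count again.

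The documents do not say how long a rescue effect lasts. These dates show which counts re-enter, not that those counts are still affected.

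**5. Illustration of size, resting on an assumption.** Inputs from Protocol Appendix 2 are response rates p = 0.20, 0.40, 0.55 and 0.70, and conversion of non-responders after titration c = 0.25, 0.25 and 0.33, with none at 1500 mg.

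Never-responders = 1 − [p + (1 − p)c]:
- 75 mg: 1 − (0.20 + 0.80 × 0.25) = 0.60
- 225 mg: 1 − (0.40 + 0.60 × 0.25) = 0.45
- 675 mg: 1 − (0.55 + 0.45 × 0.33) = 0.30
- 1500 mg: 1 − 0.70 = 0.30

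Assume a fraction f of never-responders starts other ITP therapy and reaches a qualifying count. The documents give no value for f. The added rate is f × never-responders.

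| f | 75 mg | 1500 mg | Gap, 1500 minus 75 mg |
|---|---|---|---|
| 0 | 0.40 | 0.70 | 0.30 |
| 0.10 | 0.40 + 0.06 = 0.46 | 0.70 + 0.03 = 0.73 | 0.27 |
| 0.40 | 0.40 + 0.24 = 0.64 | 0.70 + 0.12 = 0.82 | 0.18 |

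The narrowing of the gap follows from using the same f in every cohort.

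**6. Is non-rescue ITP therapy contemplated at all?** The visible text treats it as distinct from rescue in several places. The stopping rule names rescue and concomitant therapy separately. Protocol Section 4 gives background therapy and rescue medications as separate examples. Protocol 5.4.2 assesses corticosteroid dependence. SAP 7.3.4 lists current medication and, additionally, rescue medication. None of this shows how often such therapy is started or increased on study.

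**The case against.** **Standard of care.** A reader might infer from Protocol 3.2 that subjects receive standard ITP care during follow-up, so that misattributed responses must occur. The text does not support this. The sentence is untimed, sits under a post-study heading, and follows a separate sentence about the extension.

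**Redaction.** The restrictions on other treatment are in Protocol Section 3.4, which is blacked out. Protocol 1.5.3 says concurrent systemic immune-modulating agents are prohibited or restricted. New ITP therapy may be barred through follow-up, or may all be classed as rescue. Section 1.5.5 is a risk paragraph rather than a definition, and it adds that rescue is meant to raise platelet counts, which could cover more than acute use. This stands: the frequency cannot be established, and the redaction is not a fault in the plan. What remains is that the visible SAP rule names rescue only and expires after 28 days.

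**The protocol's window.** By-phase rates under Protocol 8.4.2 cannot be affected by treatment started after Day 85. The adaptive dose models are described in terms of response to starting and titration doses, not follow-up. Both points stand, and both limit the harm. But the SAP specifies whole-study response in place of the by-phase rates, and treatment started after early discontinuation but before Day 85 could still affect a by-phase rate.

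**Re-treatment after relapse.** A reader might infer that a subject who loses response and is then re-treated counts as having maintained it. Protocol 5.4.2 ends duration at loss of R or CR, so later treatment does not restore it. The gap concerns therapy started or increased while the subject is still in response.

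**Existing listings.** The study is descriptive, and medications, rescue use and daily counts are listed, so individual cases could be found. That helps a reader of the listings but does not correct the tabulated rates.

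**Conclusion.** The point holds as a gap in the analysis rule, not as a demonstrated bias. Followed as written, the SAP can credit BMS-986004 with responses due to newly started or increased non-rescue ITP therapy, and with counts that re-enter after the rescue flag lapses. Its whole-study window also departs from Protocol 8.4.2, and its exclusion is narrower than the protocol's own stopping rule.

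The firm figure is 10 points per misattributed responder in a cohort of 10. The rise of 6 to 24 points at 75 mg, and the gap falling from 30 points to between 27 and 18, are illustrations that rest on the assumed 10% to 40%. If no such therapy is given, or if all of it is flagged as rescue and its effect ends within 28 days, the bias is zero. The change is worth making because the endpoint is uncontrolled, the cohorts are small and the correction is cheap.

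**What to change.** 1. In SAP 7.5.1, extend the exclusion flag to any ITP-directed therapy newly started or increased after Day 1, including splenectomy. From its start, do not use later counts for R, CR, clinically significant response, time to peak or percent of visits.
2. For duration of response and off-drug maintenance, treat the start of such therapy while the subject is still in response as the end of response. A loss seen earlier already ends it under Protocol 5.4.2.
3. Report response rate by response phase and remission phase, as Protocol 8.4.2 states. Give the whole-study, all-counts version as a sensitivity analysis.
4. Reconcile the SAP's 4-week follow-up with the protocol's 8 weeks, so that it is clear which off-drug counts are in the data.

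The cost is SAP wording and one derived flag, built from medication and procedure data that SAP 7.3.4 and 7.3.5 already list. Patient care does not change. Reported response may be slightly lower and fewer follow-up counts will be assessable. A subject treated early with another therapy who later responds on study drug would lose that credit in the main analysis; the all-counts version would still include the response. Subjects with assessable counts before such therapy keep a response status from those counts.

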3.3 Study Population

For entry into the short-term period of the study, the following criteria **MUST** be met prior to dosing on Day 1 of the Short Term Period. No exceptions will be granted.

For entry into the long term extension, subjects must remain on study medication, complete the short-term period (up to 12 weeks of treatment), qualify per guidance for an increase in platelet count and safety, and sign a new informed consent.

3.3.1 Inclusion Criteria

1. Signed Written Informed Consent

- a) The signed written informed consent form must be obtained from the subject in accordance with requirement of the study center's IRB, prior to initiation of any protocol required procedures.

2. Target Population

- a) Adults (≥ 18 years old), diagnosed with persistent or chronic ITP according to American Society of Hematology (ASH)/British Committee for Standards in Haematology (BCSH) guidelines, with or without prior splenectomy.
- b) Subjects previously received one or more prior ITP therapies and must have had initially responded to at least one prior ITP therapy. Previous treatments for ITP include but are not limited to TPO mimetics/agonists, corticosteroids, immunoglobulins, azathioprine, danazol, cyclophosphamide and/or rituximab.
- c) Subjects have had relapsed ITP i.e. failed to achieve a sustained (for more than 3 month) platelet count $\geq 50,000/\text{mm}^3$ to at least one prior ITP therapy.
- d) The platelet count (calculated from the mean of the 2 counts taken within a week of the first dose, during the screening and pre-treatment periods) must be less than $30,000/\text{mm}^3$ with no count greater than $35,000/\text{mm}^3$. If the mean of the counts is between $30,000$ - $35,000/\text{mm}^3$, the subject may still be eligible but enrollment will be on a case by case basis and require approval by the Study Director.
- e) Subject Re-enrollment: This study permits the re-enrollment of a subject that has discontinued the study as a pre-treatment failure (ie, subject has not been randomized / has not been treated). If re-enrolled, the subject must be re-consented.
- f) A complete blood count must be within the reference range (including white blood count [WBC] differential not indicative of a disorder other than ITP), with the following exceptions:
 - i) subjects with hemoglobin levels between 9 g/dL for females and 10 g/dL for males and the lower limit of normal (LLN) are eligible for inclusion, if anemia was clearly attributable to ITP (excessive blood loss);
 - ii) absolute neutrophil count (ANC) greater than or equal to $1500/\mu\text{L}$ (elevated WBC/ANC due to corticosteroid treatment is acceptable)
- g) Prothrombin Time/International Normalized Ratio (PT/INR) and activated partial thromboplastin time (aPTT) must have been within 80% to 120% of the normal range with no known hypercoagulable state.
- h) The following clinical chemistries MUST NOT exceed 2 times the normal reference range: ALT, AST, alkaline phosphatase, and bilirubin >1.5 times upper limit normal (ULN) (isolated bilirubin $>1.5 \times \text{ULN}$ is acceptable if bilirubin is fractionated and direct bilirubin is $<35\%$)
- i) Albumin must be within 80 to 120% of normal range

3. Age and Reproductive Status

- a) Males and Females, ≥ 18 years old.
- b) Women of childbearing potential (WOCBP) must have a negative serum or urine pregnancy test (minimum sensitivity 25 IU/L or equivalent units of HCG) within 24 hours prior to the start of study drug.
- c) Women must not be breastfeeding
- d) WOCBP must agree to follow instructions for method(s) of contraception for the duration of treatment with study drug (84 days) plus 5 half-lives of study drug (20 days) plus 30 days (duration of ovulatory cycle) for a total of 134 days post-treatment completion.
- e) Males who are sexually active with WOCBP must agree to follow instructions for method(s) of contraception for the duration of treatment with study drug (84 days) plus 5 half-lives of the study drug (20 days) plus 90 days (duration of sperm turnover) for a total of 194 days post-treatment completion.
- f) Azoospermic males and WOCBP who are continuously not heterosexually active are exempt from contraceptive requirements. However they must still undergo pregnancy testing as described in this section.

Investigators shall counsel WOCBP and male subjects who are sexually active with WOCBP on the importance of pregnancy prevention and the implications of an unexpected pregnancy. Investigators shall advise WOCBP and male subjects who are sexually active with WOCBP on the use of highly effective methods of contraception. Highly effective methods of contraception have a failure rate of $< 1\%$ when used consistently and correctly.

At a minimum, subjects must agree to the use of one method of highly effective contraception as listed below:

HIGHLY EFFECTIVE METHODS OF CONTRACEPTION

- Male condoms with spermicide
- Hormonal methods of contraception including combined oral contraceptive pills, vaginal ring, injectables, implants and intrauterine devices (IUDs) such as Mirena® by WOCBP subject or male subject's WOCBP partner. Female partners of male subjects participating in the study may use hormone based contraceptives as one of the acceptable methods of contraception since they will not be receiving study drug
- IUDs, such as ParaGard®
- Tubal ligation
- Vasectomy
- Complete Abstinence*

*Complete abstinence is defined as complete avoidance of heterosexual intercourse and is an acceptable form of contraception for all study drugs. Female subjects must continue to have pregnancy tests. Acceptable alternate methods of highly effective contraception must be discussed in the event that the subject chooses to forego complete abstinence

